### **10.1.3 Recording and Reporting of Serious Adverse Events**

Every SAE (regardless of severity and causality) that occurs once the caregiver/patient has signed the ICF and until the post-treatment follow-up (Visit 10), and 28 days after the final dose of study drug, should immediately and not later than within 24 hours of knowledge of the event, be reported by the investigator or delegate in the SAE report form.

Report of a SAE must include at least the following information:

- Patient identification information (study number, site number, initials, and date of birth [as per local country requirements for data protection])
- The last study drug administration date
- The diagnosis of the event with the description (or a brief description of signs/symptoms/clinical course if the diagnosis is not available) and the date of onset
- The action used to treat the event (i.e., treatment medications, temporary discontinuation)
- The reason(s) for considering the event serious
- The relationship of the event to the study drug or to the study procedure (e.g., the investigator's assessment of causality)
- A brief narrative of the SAE

Follow-up reports including all new information obtained of the subsequent course of the SAE must be prepared and the information collected in the SAE submitted to [REDACTED] [REDACTED] [REDACTED] (Pharmacovigilance and Safety Services Department) by e-mail within 24 hours of knowledge of the event.

The pharmacovigilance manager (PVM) may contact the investigator to obtain further information on a reported SAE. The investigator/investigative staff must respond to any

request for follow-up information or answers to questions regarding the SAE within the same timelines as for initial reports.

The PVM reports the occurrence of the SAE and follow-up to the Albireo medical monitor for medical assessment of the case.

Should an outcome of death occur within the study period or within 28 days after the last administration of study drug, an SAE form should be completed including the main and contributory causes of death.

All SAE reports must be e-mailed to the following e-mail address within **24 hours**:

[REDACTED]

[REDACTED]

If email is unavailable, SAEs may be transmitted via fax to the following number:

[REDACTED]

In a study-related medical emergency situation, when the assigned medical monitors for the study cannot be reached by a caller, an on call physician can be reached 24 hours per day, 7 days per week, via the [REDACTED] call center. The following number is a chargeable telephone number allowing a global reach from both landlines and mobile phones and the internet page indicated below contains a list of country-specific toll-free telephone numbers that is provided. It should be noted that not all countries globally have access to toll-free numbers as indicated on the “24/7 Medical Help desk” index. Countries without toll-free numbers need to dial the chargeable number as indicated below. Furthermore, toll-free numbers might not be available from mobile phones.

[REDACTED]

[REDACTED]

#### **10.1.4 Reporting of Suspected Unexpected Serious Adverse Reactions**

Suspected unexpected serious adverse reaction (SUSAR) is an SAE that occurs in a patient, the nature or severity of which is not expected per the applicable product information (e.g., the IB for an unauthorized investigational product or summary of product characteristics for an authorized product).

Reporting and tracking of SUSARs will be in accordance to all applicable competent authority regulations. The Ethics Committee and all investigators involved in this study will be informed according to national and international requirements.

## **10.2 Laboratory Values/Vital Signs/Physical Examinations and Other Safety Assessments**

### **10.2.1 Laboratory Assessments**

Samples will be collected for clinical chemistry, hematology, and urinalysis testing at the time points specified in [Table 1](#). The parameters assessed are presented in [Table 3](#).

Blood for AFP will be drawn at Visits 3 and 9. Fat-soluble vitamin levels including vitamins A and E, and 25-hydroxy vitamin D will be drawn at Visit 2 (vitamins A & E only), Visit 3 (25-hydroxy vitamin D only), Visit 6, and Visit 9. Blood for INR (surrogate for vitamin K) will be drawn at Visits 2, 4, 6, 8, and 10. Patients will fast (water intake only is permissible) for at least 4 hours prior to the collection of samples for vitamin A. Exceptions can be made for infants, <12 months of age, if unable to fast for the full 4 hours. If a patient has any vitamin level(s) that are outside of the reference range, vitamin supplementation adjustments may be required. Target ranges and supplementation strategy guidelines can be found in [Appendix 5](#).

A serum pregnancy test will be performed at Visit 1 and Visit 9 if the patient is entering the A4250-008 study. A urine pregnancy test will be collected at all other visits for girls who have reached menarche. If a urine pregnancy test is positive, a serum pregnancy test should be performed to confirm the pregnancy. Study drug administration will be held pending the confirmatory results. If the serum pregnancy test is negative, the patient can resume dosing. If the serum pregnancy test is positive, the patient should be discontinued (see [Section 10.2.9](#)).

All samples will be processed and transported to a laboratory per instructions in the laboratory manual.

The observed values will be recorded and assessed as “normal” or “abnormal not clinically significant” or “abnormal clinically significant”.

Additional safety blood samples may be needed due to follow-up of an abnormal value or analysis failure. The blood samples collected for safety laboratory analysis will be destroyed after the analyses have been completed.

**Table 3 Routine Laboratory Parameters**

Clinical Chemistry	Hematology	Urinalysis

 
• Albumin
 
• ALT
 
• Alkaline phosphatase
 
• AST
 
• Bilirubin – total and direct
 
• Calcium
 
• Chloride
 
• Creatinine
 
• Creatine kinase
 
• Gamma-glutamyl transferase
 
• Potassium
 
• Sodium
 
	
 
• Hematocrit
 
• Hemoglobin
 
• Platelet count
 
• Red blood cell count
 
• White blood cell count and differential (neutrophils, eosinophils, basophils, lymphocytes, and monocytes)
 
	
 
• Blood
 
• Glucose
 
• Ketones
 
• Leukocytes
 
• Nitrites
 
• pH
 
• Protein
 

## 10.2.2 Individual Patient Safety Monitoring

### 10.2.2.1 Liver Monitoring

Strategies to monitor markers of liver disease throughout the study are outlined below where the ULN will be based on central laboratory reference values for age and gender.

**If isolated transaminase elevations are observed, defined as:**

1. Normal bilirubin AND absence of clinical hepatitis symptoms AND
  - ALT or AST  $\geq 5 \times$  ULN (if normal at baseline) or an absolute threshold of 800 U/L, whichever comes first
  - OR ALT or AST  $\geq 3 \times$  baseline (if abnormal at baseline) or an absolute threshold of 800 U/L, whichever comes first

Then:

- a) Repeat liver profile (AST, ALT, bilirubin, and prothrombin time [PT] or INR) within 2 to 3 days
- b) Evaluate creatine phosphokinase (CPK) and lactate dehydrogenase (LDH)
- c) As needed (for example, persistent ALT/total bilirubin elevation or worsening of liver function), consider evaluation for alternative etiologies

Monitor the patient using close observation found in [Section 10.2.2.2](#)

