**If any ONE of the following criteria are met:**

1. Transaminases (ALT or AST  $\geq 3 \times$  baseline or 800 U/L, whichever comes first) AND bilirubin (total bilirubin  $> 2 \times$  ULN) elevations

2. Transaminase elevations alone (ALT or AST  $>10 \times$  ULN or  $5 \times$  baseline or absolute threshold of 800 U/L, whichever comes first) in presence of normal LDH and CPK
3. Total bilirubin increased, unrelated to hemolysis (elevated reticulocyte count) or established genetic diseases, such as Gilbert's syndrome
  - a. Doubling if total bilirubin was  $<3$  mg/dL (equivalent to  $51.3 \mu\text{mol/L}$ ) at baseline
  - b. OR Increase by  $>3$  mg/dL (equivalent to  $51.3 \mu\text{mol/L}$ ) if total bilirubin was  $\geq 3$  mg/dL (equivalent to  $51.3 \mu\text{mol/L}$ ) at baseline
4. INR increase refractory to vitamin K administration
  - a. INR  $>1.5$  if INR was normal at baseline
  - b. OR Increase by  $>0.4$  if INR was abnormal at baseline
5. Any increase in total bilirubin and transaminases if accompanied by EITHER a symptom of clinical hepatitis (e.g., vomiting, nausea, right upper quadrant pain) OR immunological reaction (rash or  $>5\%$  eosinophilia)

Then:

- a) Interrupt study medication
- b) Initiate drug-induced liver injury work-up for alternative etiologies
- c) Repeat liver profile (AST, ALT, total bilirubin, direct bilirubin) and PT or INR within 48 to 72 hours
- d) Monitor the patient using close observation found in [Section 10.2.2.2](#)
- e) If a patient lives in a remote area, they may be tested locally and the results communicated to the investigator site promptly

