#### **10.2.2.2 Close Observation**

- Repeat liver enzyme and serum bilirubin tests two or three times weekly. Frequency of re-testing can decrease to once a week or less if abnormalities stabilize or the trial drug has been discontinued and the subject is asymptomatic
- Obtain a more detailed history of symptoms and prior or concurrent diseases
- Obtain a history of concomitant drug use (including non-prescription medications and herbal and dietary supplement preparations), alcohol use, recreational drug use, and special diets
- Consider ruling out alternate etiology including acute viral hepatitis types A, B, C, D, and E; autoimmune or alcoholic hepatitis; non-alcoholic steatohepatitis; hypoxic/ischemic hepatopathy; and biliary tract disease
- Obtain a history of exposure to environmental chemical agents.

- Obtain additional tests to evaluate liver function, as appropriate (e.g., INR, direct bilirubin)
- Consider gastroenterology or hepatology consultations.

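### Liver rules leave a hole: an ALT/AST rise of at least 3×baseline with bilirubin between 1 and 2×ULN can trigger no specified action, although the same rise with normal bilirubin does

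*Protocol*

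**What the plan says.** Section 10.2.2.1 (Protocol of 24 June 2019) has two lists. ULN is the central laboratory value for age and gender.

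- **Close-observation tier.** Entry requires "Normal bilirubin AND absence of clinical hepatitis symptoms AND" ALT or AST of at least 5×ULN (normal baseline), at least 3×baseline (abnormal baseline), or 800 U/L. The actions are a repeat liver profile in 2 to 3 days, CPK and LDH, and close observation. Under section 10.2.2.2 that means: "Repeat liver enzyme and serum bilirubin tests two or three times weekly".
- **Interruption list, any one of five criteria.** Criterion 1 sets ALT/AST at 3×baseline or 800 U/L, "whichever comes first) AND bilirubin (total bilirubin", with the bilirubin limit at more than 2×ULN. Criterion 2 begins "Transaminase elevations alone (ALT or AST" and sets more than 10×ULN, 5×baseline or 800 U/L, but only "in presence of normal LDH and CPK". Criterion 3 needs bilirubin to double (baseline below 3 mg/dL) or to rise by more than 3 mg/dL. Criterion 4 needs an INR increase refractory to vitamin K. Criterion 5 starts "Any increase in total bilirubin and transaminases if accompanied by EITHER a symptom of clinical hepatitis" or an immunological reaction.

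Table 3 lists "Creatine kinase" in routine chemistry but not LDH. The same rules stand in the versions of 29 April 2019 and 1 March 2019.

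**The concern.** The tier stops at 1×ULN of bilirubin and criterion 1 starts above 2×ULN, at the same 3×baseline limit for a child with abnormal baseline transaminases. Unless another criterion covers the interval, the response is not ordered by severity: a mildly raised bilirubin earns less specified action than a normal one.

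Such children can be in the trial. Section 5.2.1 describes hyperbilirubinemia with raised ALT and AST as the usual biochemistry of the disease, and the screening limits are 10×ULN for both ALT and bilirubin (exclusion criteria 12 and 14). *Normal* bilirubin cannot be read as the child's own usual level: the tier adjusts ALT and AST for an abnormal baseline but not bilirubin.

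At stake is how soon a possible drug-induced liver signal is retested. The tier fixes 2 to 3 days. Outside it, the only fixed times are the scheduled chemistry samples.

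**Working it through.** There is no stated figure to reproduce; the check applies the rules as written.

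**Notation.** b = baseline ALT (or AST) and a = current value, both in ×ULN; t = current total bilirubin in ×ULN; U = ALT ULN in U/L. The protocol does not give U, so 40, 50 and 60 U/L are assumed.

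**Rules (section 10.2.2.1)**

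- Tier: t ≤ 1, no hepatitis symptoms, and a ≥ 5 (if b ≤ 1), or a ≥ 3b (if b > 1), or aU ≥ 800.
- Criterion 1: (a ≥ 3b or aU ≥ 800) and t > 2.
- Criterion 2: (a > 10 or a ≥ 5b or aU ≥ 800), with LDH and CPK normal.
- Criteria 3, 4 and 5: not met if bilirubin and INR are unchanged.

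**One child at three bilirubin levels.** b = 1.5, a = 6, so a/b = 4. Then 3b = 4.5 is reached, 5b = 7.5 is not, 10×ULN is not, and aU is 240, 300 or 360 U/L, below 800. No symptoms, bilirubin and INR unchanged.

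| Bilirubin | Rule met | Specified action |
|---|---|---|
| 0.95×ULN | Tier | Profile in 2 to 3 days, CPK/LDH, close observation |
| 1.5×ULN | None | None |
| 2.1×ULN | Criterion 1 | Interrupt drug, work-up, profile in 48 to 72 hours |

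Stable bilirubin is not essential. A rise from 0.9 to 1.7×ULN is a factor of 1.7/0.9 = 1.89: not doubled and not above 2×ULN. Without symptoms or an immunological reaction, still no rule applies.

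**Extent (a): LDH and CPK normal, t = 1.5.** The hole runs from 3b up to, but not including, 5b, or to 10×ULN if that is lower.

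| b | Uncovered ALT (×ULN) |
|---|---|
| 1.2 | 3.6 to <6 |
| 1.5 | 4.5 to <7.5 |
| 2 | 6 to <10 |
| 2.5 | 7.5 to 10 |
| 3 | 9 to 10 |

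It closes once 3b > 10, that is b above 10/3 = 3.33. For b ≤ 1 it is empty, because a ≥ 5 is then also a ≥ 5b and criterion 2 applies. The 800 U/L limit would matter only if U exceeded 800/10 = 80.

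**Extent (b): LDH or CPK abnormal, or LDH not measured.** Criterion 2 cannot then be counted as met. The lower edge becomes 5×ULN for b ≤ 1, 4.5 at b = 1.5, 3 × 3.4 = 10.2 at b = 3.4, and 3 × 4 = 12 at b = 4. At b = 5 it is 15, or 800/60 = 13.3 if U = 60. There is no upper edge, because the 800 U/L limit in criterion 2 carries the same LDH/CPK condition. Reading *alone* in criterion 2 as excluding raised bilirubin has the same effect; the text does not define it. LDH is ordered as an action only inside the normal-bilirubin tier, which this child does not enter.

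**Symptoms.** With hepatitis symptoms and bilirubin unchanged or lower, the tier is closed (it requires no symptoms) and so is criterion 5 (it requires a bilirubin increase). The same ALT bands are then uncovered, at normal bilirubin as well as at 1.5×ULN.

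**Retest interval.** Table 1 schedules on-treatment chemistry on Days 28, 56, 84, 126 and 168 after Day 0, giving intervals of 28, 28, 28, 42 and 42 days. Visit 8 (Day 154) has INR but no chemistry.

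**The case against.** The strongest reply has four parts.

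- **The band is narrow.** With LDH and CPK normal it needs a particular baseline, a particular size of rise, bilirubin between 1 and 2×ULN that has not doubled, and no INR trigger. This is correct, and it limits the weight of the point. It does not remove the inverted ordering.
- **Branch (b) looks larger than it is.** A site facing more than 10×ULN or 800 U/L would have to obtain LDH to apply criterion 2, and section 10.2.1 allows extra samples. Where LDH or CPK is truly abnormal, withholding automatic interruption is intended. Both points are fair. What is missing in that case is close observation, the same defect as in (a).
- **The symptom case is close to a knife edge.** Any bilirubin increase at all brings criterion 5 into play, so only unchanged or falling bilirubin is left out. That is so, and it makes this part secondary.
- **Clinical care does not stop at the table.** Values are assessed for clinical significance and extra samples may be drawn (10.2.1), worsening can be an AE (10.1.1.1, 10.1.2), extra visits are possible (7.1.1), the investigator may withdraw a patient (7.2.3), and the DSMB reviews liver values about quarterly (11.2.4). These provisions are real, but none sets a prompt retest or orders LDH. Section 10.2.2.1 exists to fix those actions.

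**Conclusion.** The concern holds. As written, an asymptomatic child with abnormal baseline ALT/AST, a rise of at least 3 but below 5×baseline that stays at or below 10×ULN and under 800 U/L, and bilirubin above 1 and up to 2×ULN without doubling meets no rule. The same rise at normal bilirubin does meet one. This band does not depend on how criterion 2 is read, nor on U while U is below 80 U/L. The wider extent depends on LDH or CPK being abnormal or unavailable, or on a strict reading of *alone*.

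The protocol gives no frequency for this combination, so the number of children affected is unknown. No endpoint, analysis or sample size changes. It should be fixed as a modest safety correction.

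**What to change.** In section 10.2.2.1:

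1. In the close-observation tier, replace the normal-bilirubin condition by total bilirubin of 2×ULN or less, so that the tier meets criterion 1.
2. State that interruption takes precedence once any interruption criterion is met. Entry to the tier then does not depend on LDH, and the LDH and CPK ordered there decide criterion 2.
3. Send a child with hepatitis symptoms and the same ALT/AST rise, but no bilirubin increase, at least to close observation.
4. Define *alone* in criterion 2, for example as bilirubin not above the criterion 1 limit, and adjust the tier's heading, since it would no longer cover only isolated elevations.

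Changes 1 to 3 close the hole. At 2×ULN or below, every rise reaching the tier limit enters the tier. Above 2×ULN criterion 1 catches it, because 5×ULN from a normal baseline is also at least 3×baseline. Change 4 settles whether a large rise at bilirubin 1 to 2×ULN calls for interruption or observation.

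Cost: a few phrases, but a change to safety triggers is neither logistical nor administrative, so section 13.1 requires a formal amendment with competent authority and IEC/IRB approval. Sites need notice. The affected children have extra liver profiles and CPK/LDH, with testing two or three times weekly until values stabilise. That blood volume deserves a check in the smallest patients, since entry is allowed just above 5 kg.

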**If any ONE of the following criteria are met:**

1. Transaminases (ALT or AST  $\geq 3 \times$  baseline or 800 U/L, whichever comes first) AND bilirubin (total bilirubin  $> 2 \times$  ULN) elevations

2. Transaminase elevations alone (ALT or AST  $>10 \times$  ULN or  $5 \times$  baseline or absolute threshold of 800 U/L, whichever comes first) in presence of normal LDH and CPK
3. Total bilirubin increased, unrelated to hemolysis (elevated reticulocyte count) or established genetic diseases, such as Gilbert's syndrome
  - a. Doubling if total bilirubin was  $<3$  mg/dL (equivalent to  $51.3 \mu\text{mol/L}$ ) at baseline
  - b. OR Increase by  $>3$  mg/dL (equivalent to  $51.3 \mu\text{mol/L}$ ) if total bilirubin was  $\geq 3$  mg/dL (equivalent to  $51.3 \mu\text{mol/L}$ ) at baseline
4. INR increase refractory to vitamin K administration
  - a. INR  $>1.5$  if INR was normal at baseline
  - b. OR Increase by  $>0.4$  if INR was abnormal at baseline
5. Any increase in total bilirubin and transaminases if accompanied by EITHER a symptom of clinical hepatitis (e.g., vomiting, nausea, right upper quadrant pain) OR immunological reaction (rash or  $>5\%$  eosinophilia)

Then:

- a) Interrupt study medication
- b) Initiate drug-induced liver injury work-up for alternative etiologies
- c) Repeat liver profile (AST, ALT, total bilirubin, direct bilirubin) and PT or INR within 48 to 72 hours
- d) Monitor the patient using close observation found in [Section 10.2.2.2](#)
- e) If a patient lives in a remote area, they may be tested locally and the results communicated to the investigator site promptly

#### **10.2.2.2 Close Observation**

- Repeat liver enzyme and serum bilirubin tests two or three times weekly. Frequency of re-testing can decrease to once a week or less if abnormalities stabilize or the trial drug has been discontinued and the subject is asymptomatic
- Obtain a more detailed history of symptoms and prior or concurrent diseases
- Obtain a history of concomitant drug use (including non-prescription medications and herbal and dietary supplement preparations), alcohol use, recreational drug use, and special diets
- Consider ruling out alternate etiology including acute viral hepatitis types A, B, C, D, and E; autoimmune or alcoholic hepatitis; non-alcoholic steatohepatitis; hypoxic/ischemic hepatopathy; and biliary tract disease
- Obtain a history of exposure to environmental chemical agents.

- Obtain additional tests to evaluate liver function, as appropriate (e.g., INR, direct bilirubin)
- Consider gastroenterology or hepatology consultations.

#### **10.2.2.3 De-challenge/Re-challenge for Liver and Clinical Hepatitis Monitoring**

1. Re-challenge is not recommended:
  - a. If a patient has had possible/probable drug-induced liver injury
  - b. If a decompensation event has occurred (i.e., variceal hemorrhage, ascites, hepatic encephalopathy, etc.).
2. If due to underlying cholestatic liver disease variability or another alternative etiology is identified AND liver tests returned to baseline, re-challenge may be considered after consultation with the sponsor Medical Monitor.
3. If the ALT/total bilirubin elevations are observed after re-challenge, then repeat re-challenge is discouraged.

If patient is permanently discontinued, monitoring should be continued as outlined in [Section 10.2.2.5](#).

#### **10.2.2.4 Diarrhea**

Study drug should be discontinued if a patient develops diarrhea with at least 1 of the following concomitant signs or symptoms: grossly bloody stools, vomiting, dehydration requiring treatment with oral or intravenous rehydration and/or electrolyte imbalances, fever ( $\geq 38$  C) and/or the diarrhea persists for 7 or more days.

If there is gross blood in stool, INR and platelets should be measured.

Study drug will be reintroduced (re-challenge) when the symptoms have resolved. If the diarrhea re-occurs within 1 week after the re-challenge with no alternate etiology, the patient will be permanently discontinued and monitored as outlined in [Section 10.2.2.5](#).

#### **10.2.2.5 Monitoring after Permanent Discontinuation of Study Drug Due to Safety**

Once study drug is permanently discontinued for liver, hepatitis, diarrhea, or other severe AE related to study drug, the patient will be monitored weekly until the laboratory and clinical parameters have normalized/stabilized.

### **10.2.3 Demographics/Medical and Surgical History**

Demographic information per country regulations (age, full date of birth, gender, race, and ethnicity), along with medical and surgical history, will be obtained and recorded in the eCRF at Visit 1.

Medical and surgical history will be entered in the eCRF at Visit 1. This includes date of diagnosis of PFIC, prior investigational medications for PFIC, historical (3 months prior to

Screening) LFT values (AST, ALT, and total bilirubin), ongoing medication, any surgery performed, any other diagnosis, and historical biopsy data.

If a liver biopsy has been performed within 1 year prior to Screening, or during the study, the results will be recorded in the eCRF.

#### **10.2.4 Clinical Genetic Testing**

For previous confirmatory clinical genetic testing results for PFIC Type 1 or 2 performed prior to Screening Visit 1, the confirmatory clinical genetic testing laboratory report will be verified to determine eligibility.

If the historical clinical genetic result is equivocal, unavailable, or unobtainable, clinical genetic analysis to confirm pathologic biallelic variations in the *ATP8B1* or *ABCB11* genes will be performed and verified to determine eligibility. No other diagnostic genetic testing will be offered.

